Enrolled patients and their families will be randomized 1:1 after discharge to the intervention group or standard-of-care using a permuted block randomization stratified by acute versus chronic underlying illness and hospitalist service general vs. surgical service to ensure equal allocation of the intervention within each stratification block. Random permutations within each block within each stratum will be generated using a random number generator available in SAS Proc Plan. The use of randomization in the study design is crucial for avoiding bias in the evaluation of the effectiveness of the nurse home visit intervention. Patients and families cannot be blinded given that the nature of the intervention is a nurse home visit. However, we will attempt to mitigate the potential bias in the following manner: 1) Families will be asked to refrain from disclosing intervention status to the interviewer at the follow-up phone call; and 2) Study staff will be blinded to treatment assignment when making the follow-up phone call. Study staff will use a written script to administer the survey. At the start of the call, families will be reminded to refrain from disclosing their intervention status.

Heterogeneity of Treatment Effects:

We have multiple planned analyses to examine potential heterogeneity of treatment effect of the nurse visit. Factors included in the HET analysis are insurance, primary care access, financial strain, caregiver education, hospital service, and medical complexity. Medical complexity will be determined by the pediatric medical complexity algorithm (PMCA). The PMCA is a publicly available algorithm that identifies children with complex chronic disease (who have accessed tertiary hospital care). The algorithm includes three levels of medical complexity: children with complex chronic disease (C-CD), children with non-complex chronic disease (NC-CD), and children without chronic disease (CD). In order to calculate the PMCA we will collect additional administrative data for all patients enrolled in Aims 3 and 4. This data will include: ICD9 Codes/ICD10 codes, procedure codes, admission date, discharge dates, admitting and discharge departments. We will capture all outpatient, urgent care, ED, and hospital events within the specified time window (February 1, 2012 to April 30, 2016). The PMCA will be calculated based on a 3-year window before the index hospitalization.

Aim 4

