Initial Questionnaire: Face-to-face interviews will be conducted in the hospital with the parent or caregiver at the time of enrollment. We will assess demographic characteristics, such as race, ethnicity, and age for both the parent/caregiver and patient. We will assess parent or caregiver marital status, education, household income, employment status, resilience, and parental activation. In addition, we will assess the ACE (adverse childhood experience) score of parents ages 18 years or older. The ACE score is a measure of childhood trauma that has occurred in the past. It does not indicate current exposure. Higher scores (ACE score greater than or equal to 4) have been associated with poorer adult health outcomes. Parental ACE scores have demonstrated an association with risk for childhood adversity in an outpatient setting. The questions encompass all forms of childhood trauma, including whether the participant was exposed to a household member that was depressed or suicidal or if the participant had been abused as a child. The ACE questionnaire will be provided as a handout for the study participant to fill out. It will be supplemented with a handout with the contact information of an inpatient social worker. It will be returned by the study participant in a sealed envelope to the research coordinator. It may be left blank by the study participant if they choose not to answer the questions. We will also assess the patient's medical history and their access to primary care, as well as other variables that arise from Aims 1 and 2. Survey data will be entered into a password protected electronic database.

Aim 3 Nurse Home Visit Intervention: The intervention for Aim 3 is a revised nurse home visit. This intervention will build upon the baseline nurse home visit program by incorporating approaches to effectively address barriers to transition as determined in Aims 1 and 2. The current program involves a *single* nurse home visit within 96 hours after discharge and includes

physical and self-management assessment with the goal of ensuring patient stability and caregiver confidence. While we expect that many elements and processes of the current nurse home visit will remain intact, in Aim 1 we will be assessing current users' perceptions of the services as well as better defining the patient- and family- desired outcomes. In Aim 2, we will test small changes to the home visit elements and processes as informed by Aim 1 results.

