Aim 4 Nurse Phone Call Intervention: The intervention for Aim 4 is a revised nurse phone call. This intervention will closely resemble the existing nurse home visit intervention currently being studied. The current program involves a *single* nurse home call within 96 hours after discharge and includes physical and self-management assessment with the goal of ensuring patient stability and caregiver confidence. While we expect that many elements and processes of the current nurse home visit will remain intact, in the optimization phase we will be assessing early users' perceptions of the and we will test small changes to the phone call elements and processes as informed by early testing.

Follow-up Questionnaire: A follow-up questionnaire to assess 14-day post-discharge outcomes will be conducted in both the control and intervention groups 14-30 days post-discharge. All efforts will be made for the follow-up questionnaire to be completed with the same parent or caregiver who completed the initial questionnaire. If this is not possible we will re-collect demographic information for the secondary parent or caregiver completing the follow-up questionnaire. We will collect the primary outcome measures of unplanned post-discharge utilization, as well as the secondary outcomes defined during the focus groups in Aim 1, and will re-measure the parental activation. Survey data will be entered into a password protected electronic database.

For approximately 40 of our patients, the research coordinator asked the parent's race as opposed to the patient's race for Aim 3 only. We are requesting permission to contact these participants via text message and phone call to ask the patient's race. We will also be asking the patients some questions regarding their experience with the intervention (nurse home visit) in Aim 3. We are asking these additional questions in order to use this feedback for future research studies as well as to help the flow of the call.

Medical Record Review: We will receive all enrolled patients 30-day reutilization (readmission and ED revisit) data from HealthBridge. HealthBridge is an organization that receives admission and emergency room data from hospitals throughout the Greater Cincinnati area. This will allow us to track reutilization outcomes at 30-days, while completing the call with families at 14-days. This will ensure that we have similar data for our primary outcomes from all patients.

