Working hypothesis 2: Patients who receive the nurse home visit intervention will have significantly higher parent activation scores 14-days post-discharge when compared to the patients enrolled in the control group after 14 days post-discharge. For this secondary outcome, the dependent variable will be a continuous measure of parent activation. Difference in this outcome between intervention and control groups will be evaluated using one-way analysis of variance (ANOVA) using a linear model containing a treatment effect indicator. Parental activation scores will be checked for normality and data transformations will be entertained, if needed. Baseline differences will be examined between groups, again using a linear model. If, by random chance, there is a difference between the groups, the first analysis will be repeated but adding the baseline as a covariate.

The sample size was determined based on the comparisons between the control group (standard-of-care) and intervention group (nurse home visit) for the primary outcome measure, a dichotomized indicator of all cause reutilization (i.e., rehospitalization, ED revisit, or unscheduled follow-up) within 30-days post-discharge, and the secondary outcome measure, parent activation score. A sample size of **1500** patients and their families (600 standard-of-care and 600 nurse home visits) was chosen to balance precision and feasibility. Assuming the control group primary outcome rate is 0.20, this sample size allows detectable differences of 0.07 or more (a 35% reduction or more from the control group rate) with 80% power. This detectable difference is lower than differences found in prior studies of adults. The estimated utilization rate of 0.20 in the control group is based on CCHMC data that indicates hospitalist service readmission rates of 5% on the general service and 15% on the surgical service, a 10% ED revisit rate, and a 4% outpatient service utilization rate; we assume that 10% of enrolled patients will come from the surgical service.

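### Aim 3 parent activation is adjusted for its own baseline only if the arms happen to differ, which gives up precision and leaves the governing analysis undefined

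*Protocol*

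**What the plan says.** In the protocol's DATA ANALYSIS/METHODS, Aim 3, working hypothesis 2, the 14-day activation score is to be compared between arms by "one-way analysis of variance (ANOVA) using a linear model containing a treatment effect indicator". The next steps are: "Baseline differences will be examined between groups, again using a linear model." and then "If, by random chance, there is a difference between the groups, the first analysis will be repeated but adding the baseline as a covariate." No p-value or size defines a difference, and nothing says whether the repeated analysis replaces the first or sits beside it.

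The baseline score is available. Under STUDY PROCEDURES, Aims 3 and 4, the enrolment interview covers "employment status, resilience, and parental activation", and the follow-up questionnaire "will re-measure the parental activation". Enrolment takes place in hospital, and the Aim 3 design section states: "Enrolled patients and their families will be randomized 1:1 after discharge". The first score therefore precedes allocation.

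No other text brings the baseline in. The list of candidate covariates for the Aim 3 secondary analyses omits it. The SAP covers Aim 4 only and does not list parent activation as an outcome. The Aim 3 primary-outcome model (working hypothesis 1) includes the stratification variables, chronic condition and service; the activation model does not.

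**The concern.** After randomization any baseline difference is due to chance, as the protocol's own wording accepts. A check for such a difference therefore says nothing about which model is appropriate. The reason to adjust is that baseline activation probably predicts follow-up activation, and that holds whether or not the arms look balanced. Making adjustment depend on visible imbalance discards the precision gain in most trials that could be run.

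The rule also leaves a choice open after the data are seen. If the two analyses disagree, the text does not say which one answers working hypothesis 2. At stake are the width of the interval, the power for a named secondary hypothesis, and a clear statement of its error rate.

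**Working it through.** The documents give no power, standard deviation, target difference or error rate for parent activation, so there is no stated figure to reproduce. The check works in standard deviation (SD) units.

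**Inputs from the protocol.** Allocation is 1:1, with 600 per arm. The sample-size sentence also gives a total of 1500, which does not match 600 + 600. The relative standard errors below do not depend on that number.

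**Assumed inputs.** The correlation ρ between baseline and follow-up is 0.3 to 0.7. Alpha is 0.05 two-sided, which the protocol states for Aim 4 but not for Aim 3. The trigger for adjustment is p<0.05 on the baseline comparison.

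**Precision.** Adjusting for baseline multiplies the standard error by √(1−ρ²). At ρ = 0.6 this is √(1−0.36) = 0.80, a 20% cut. The per-arm number at which ANCOVA matches the unadjusted analysis of 600 is 600 × (1−ρ²). The unadjusted difference detectable with 80% power is (1.960 + 0.842) × √(2/600) = 0.162 SD; ANCOVA multiplies it by √(1−ρ²).

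| ρ | SE factor | SE cut | ANCOVA n per arm matching 600 | Detectable difference with ANCOVA (SD) |
|---|---|---|---|---|
| 0.3 | 0.954 | 5% | 546 | 0.154 |
| 0.4 | 0.917 | 8% | 504 | 0.148 |
| 0.6 | 0.800 | 20% | 384 | 0.129 |
| 0.7 | 0.714 | 29% | 306 | 0.116 |

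**Error rate of the conditional rule.** Let Zx be the standardized baseline difference and Za the ANCOVA statistic. Under the null hypothesis in large samples these are independent, and the ANOVA statistic is Zy = ρ·Zx + √(1−ρ²)·Za. Simulating 4 million pairs, with the trigger at |Zx| > 1.96, gives the type I error under each reading of the text:

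| ρ | ANOVA decides | Either result counts | Adjusted result replaces ANOVA | ANCOVA always |
|---|---|---|---|---|
| 0.3 | 5.0% | 5.1% | 4.8% | 5.0% |
| 0.4 | 5.0% | 5.1% | 4.6% | 5.0% |
| 0.6 | 5.0% | 5.1% | 4.0% | 5.0% |
| 0.7 | 5.0% | 5.1% | 3.6% | 5.0% |

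A finite-sample simulation at 600 per arm (40,000 trials) gave 3.6% at ρ = 0.7 for the replacement reading, in agreement. With a looser trigger of p<0.20, the either-counts figure rises to at most about 5.5%, and the replacement figure falls to 4.5% at ρ = 0.3 and 2.6% at ρ = 0.7.

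**Power at a true difference of 0.162 SD.** Under the replacement reading with the p<0.05 trigger, power is 80.4%, 80.7%, 81.6% and 82.1% at ρ = 0.3, 0.4, 0.6 and 0.7. With ANCOVA always, it is 83.6%, 86.4%, 93.8% and 97.5%. The conditional rule recovers little of the available gain because, with this trigger, it fires in only 5% of trials.

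**Conditional behaviour.** Among trials that do show imbalance at p<0.05, the unadjusted ANOVA rejects a true null hypothesis about 10%, 13.5%, 25% and 33% of the time at the same four correlations. In the other 95% of trials it rejects slightly less than 5% of the time, and the two average to 5.0%.

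**The case against.** The strongest objection concerns the error rate. A reader might infer that a test-then-adjust rule inflates false positives. The documents do not support that. The protocol says only that the analysis is repeated; it does not say that the adjusted result takes over. If the ANOVA decides, the overall type I error is nominal. If either result counts, the excess is about 0.1 percentage point with the assumed trigger. If the adjusted result replaces the ANOVA, the rule is conservative. This objection stands. What remains is that the protocol does not say which case applies.

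Second, the size of the precision loss rests on a correlation that the documents do not give. At 0.3 the gain is about 5%, and the 20% to 29% figures need correlations of 0.6 to 0.7. This stands as a limit on the size, though not on the direction: any non-zero correlation favours adjustment.

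Third, the change is not free. The protocol's PURPOSE OF STUDY section shows that Aim 3 results are already known, so a new main analysis would be post hoc. The follow-up questionnaire may also be answered by a different caregiver, with only demographics re-collected. For those families the two scores come from different people, and the correlation is likely to be weaker. Both points stand and shape the fix.

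Fourth, the scope is narrow: one secondary outcome of Aim 3. The omission of the strata is an inconsistency with the primary-outcome model, and its effect has not been quantified here.

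**Conclusion.** The point holds as a matter of precision and clarity. The planned main analysis of parent activation ignores a baseline measured before allocation unless the arms happen to differ. Its standard error is larger than necessary: adjustment would remove about 5%, 8%, 20% and 29% of it at assumed correlations of 0.3, 0.4, 0.6 and 0.7. The randomization strata are also missing.

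The rule is incompletely specified, since neither the trigger nor the governing analysis is stated. Across the three readings, with an assumed p<0.05 trigger and two-sided alpha of 0.05, type I error runs from 3.6% to about 5.1%. Overall false positives are not materially inflated. The conclusions on the Aim 3 primary outcome and the Aim 4 analyses in the SAP do not depend on this point.

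**What to change.** Make one ANCOVA the main analysis of parent activation: 14-day score on treatment, baseline score, chronic-condition stratum and service stratum, whatever baseline difference is observed. Drop the baseline comparison as a rule for choosing the model. Keep the unadjusted ANOVA as a sensitivity analysis.

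The cost is small, because the scores and strata are already collected. Two rules have to be written: how a missing baseline score is handled, and how families are treated when a different caregiver answers at follow-up. Because Aim 3 results are known, report the change openly as a post hoc deviation from the protocol and show both analyses side by side.

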parents or caregivers will be able to attend the focus groups given their demanding schedules, childcare priorities, and transportation barriers. Thus, we will seek to recruit 10-12 participants per group to account for the possibility of participants failing to show up as scheduled. Recruitment will take place on the hospital wards during a child's admission. We anticipate it will take approximately 2 months to recruit the 120-160 participants necessary to ensure that we have 90-110 for our focus group sample. We expect that we will reach thematic saturation by the conclusion of these groups, meaning no new ideas or themes will be generated at that point and recruitment will be suspended.

Aim 2

Eligible patients and families will be identified by frontline clinical providers, with no input from the research team. We believe that up to 600 families will participate in this Aim. Clinical research coordinators will contact all of the families that participate in this aim via phone to participate in a short follow-up call.

Clinical research coordinators will also identify up to 100 patients during this Aim that receive primary care at one of the three CCHMC primary care clinics (Pediatric Primary Care Center, Hopple Street Clinic, and Fairfield Primary Care). We will review the patient's chart to assess return visits to primary care 30-days after admission, then will call the families to confirm their recall of these visits.

For the phone call optimization, we believe that up to 150 families will participate in this Aim. These families will receive the nurse phone call within 96 hours of discharge, then will receive a phone call from a clinical research coordinator 1-7 days after the visit to complete a short phone call about their experience with the call and any feedback they may have to improve the call.

Aim 3

All patients and families that meet the above inclusion and exclusion criteria will be eligible for the study, and will be approached, depending on CRC schedule. We anticipate enrolling up to 2000 families during this aim. We will conduct planned HET analyses.

Aim 4

All patients and families that meet the above inclusion and exclusion criteria will be eligible for the study, and will be approached, depending on CRC schedule. We anticipate enrolling up to 2000 families during this aim.

Post-Hoc Analysis

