We have multiple planned analyses to examine potential heterogeneity of treatment effect of the nurse visit. Factors included in the HET analysis are insurance, primary care access, financial strain, caregiver education, hospital service, and medical complexity. Medical complexity will be determined by the pediatric medical complexity algorithm (PMCA). The PMCA is a publicly available algorithm that identifies children with complex chronic disease (who have accessed tertiary hospital care). The algorithm includes three levels of medical complexity: children with complex chronic disease (C-CD), children with non-complex chronic disease (NC-CD), and children without chronic disease (CD). In order to calculate the PMCA we will collect additional administrative data for all patients enrolled in Aims 3 and 4. This data will include: ICD9 Codes/ICD10 codes, procedure codes, admission date, discharge dates, admitting and discharge departments. We will capture all outpatient, urgent care, ED, and hospital events within the specified time window (February 1, 2012 to April 30, 2016). The PMCA will be calculated based on a 3-year window before the index hospitalization.

Aim 4

Analyses: For the primary outcome, the dependent variable will be a dichotomized indicator of any occurrence of healthcare reutilization within 30 days of hospital discharge. Differences between phone intervention and control groups on this outcome will be evaluated using logistic regression with census tract poverty and discharge service unit included in the model. Other potential covariates (e.g. baseline characteristics with large differences between groups) will be included in a secondary analysis model evaluating the effectiveness of the phone intervention. For secondary outcomes, PDCS total score and number of days back to normal routine perceived by the caregiver at 14-day post-discharge will be analyzed as continuous variables. Differences between the phone intervention and control groups will be evaluated using linear regression with census tract poverty and discharge service unit and other potential covariates included in the model.

Sample size: Assuming a 20% reutilization rate in the control group, a sample size of 750 in the control group and 450 in the phone intervention group will achieve 80% power to detect a 7.1% decrease in reutilization rate (12.9% event rate) for the phone call intervention group with alpha=0.05, allowing for 11% noncompliance.

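### Aim 3 states a total of 1500 but arms of 600 + 600 = 1200, and the 0.07 detectable difference cannot be reproduced from the inputs given for Aim 3

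*Protocol*

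**What the plan says.** In the Protocol, Data Analysis/Methods, Aim 3, the sample-size sentence opens with "A sample size of 1500 patients and their families" and continues, in the same sentence, with "patients and their families (600 standard-of-care and 600 nurse home visits) was chosen to balance precision and feasibility". The power statement follows: "Assuming the control group primary outcome rate is 0.20", then "this sample size allows detectable differences of 0.07 or more (a 35% reduction or more from the control group rate) with 80% power".

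The design has two arms. Study Design, Aim 3 says "Enrolled patients and their families will be randomized 1:1 after discharge to the intervention group or standard-of-care". Selection & Recruitment, Aim 3 adds a third figure: "We anticipate enrolling up to 2000 families during this aim".

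The Aim 3 paragraph gives no alpha, no sidedness, and no allowance for noncompliance or attrition. The Aim 4 sample-size text does: the primary-outcome calculation is "for the phone call intervention group with alpha=0.05, allowing for 11% noncompliance", and the secondary-outcome calculations add 5% attrition and a two-sided test.

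**The concern.** With two arms and equal allocation, 1500 means 750 per arm and 600 per arm means 1200. One sentence cannot mean both, and the power statement refers back to that sentence without saying which size it describes. The stated difference also looks large for either size, because far fewer patients would give 80% power for 0.20 against 0.13 at conventional settings.

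Aim 3 has finished, but the text stands in the current protocol. The Aim 3 result was unexpected, it motivates the post-hoc work, and its arms may enter the four-arm exploratory comparison in SAP section 2.4. A reader weighing that result needs to know the planned size and the effect it was meant to detect.

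**Working it through.** **Inputs**

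- Total 1500; arms 600 and 600; 1:1 allocation (Protocol, Aim 3).
- Control rate 0.20, difference 0.07 (so 0.13 in the intervention arm), power 80% (Protocol, Aim 3 sample size). The control rate agrees with its stated components: 0.9 × 5% + 0.1 × 15% + 10% + 4% = 20%.
- Alpha 0.05 two-sided: an assumption, taken from Aim 4.
- Noncompliance *c* = 11% and attrition *d* = 5%: stated only for Aim 4, and used here only as a variant.

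**Step 1: the totals.** 600 + 600 = 1200, and 1500 − 1200 = 300 unexplained.

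**Step 2: formula.** Pooled-variance normal approximation with *n* per arm, *m* = *n*(1 − *d*), diluted difference Δ = 0.07(1 − *c*), p1 = 0.20, p2 = 0.20 − Δ and p̄ = (p1 + p2)/2:

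power = Φ{ [Δ − 1.96 √(2p̄(1 − p̄)/m)] / √([p1(1 − p1) + p2(1 − p2)]/m) }

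**Step 3: check of the dilution method.** The unequal-arm form of the same formula, applied to Aim 4 (750 and 450, difference 0.071, 11% noncompliance), gives 80.4% power. That reproduces Aim 4's stated 80%.

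**Step 4: Aim 3 as written, no allowance.** p̄ = 0.165.

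- 600 per arm: (0.07 − 1.96 × 0.02143)/0.02133 = 1.31, power 90.5%.
- 750 per arm: (0.07 − 1.96 × 0.01917)/0.01908 = 1.70, power 95.5%.

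Solving for 80% power gives detectable differences of 0.061 and 0.055. A difference of 0.07 at 80% power needs 441 per arm (882 in total).

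**Step 5: with allowances.** For *c* = 11% and *d* = 5%, Δ = 0.07 × 0.89 = 0.0623.

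- *m* = 570: (0.0623 − 1.96 × 0.02219)/0.02211 = 0.85, power 80.2%.
- *m* = 712.5: (0.0623 − 1.96 × 0.01985)/0.01978 = 1.18, power 88.2%.

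| Setting (two-sided 0.05) | 600 per arm: power at 0.07 | 600 per arm: difference at 80% | 750 per arm: power at 0.07 | 750 per arm: difference at 80% |
|---|---|---|---|---|
| No allowance | 90.5% | 0.061 | 95.5% | 0.055 |
| 11% noncompliance | 82.2% | 0.068 | 89.7% | 0.061 |
| 11% noncompliance, 5% attrition | 80.2% | 0.070 | 88.2% | 0.063 |

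**Step 6: sensitivity to the assumed test, no allowance.** One-sided 0.05 moves power further from 80% (94.8% and 97.8%). A continuity correction gives 0.062 and 0.056. Two-sided alpha 0.025 gives 0.066 and 0.060.

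For 750 per arm to reach 0.070 at two-sided 0.05, one needs, for example, 20% noncompliance with 5% attrition. The documents state no such combination.

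**The case against.** A reader might infer that 0.07 fits neither size, so that the power claim is simply wrong. The documents do not support that. Alpha, sidedness and allowances are unstated for Aim 3, and the allowances that the same protocol states for Aim 4 bring 600 per arm to 0.070 and 80.2%. Even at alpha 0.025 with no allowance, 600 per arm gives 0.066, which rounds to 0.07. The supportable statement is that the figure cannot be reproduced from the inputs given for Aim 3.

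A reader might also infer that the trial was underpowered. It was not, for this effect: with no allowance both sizes exceed 80% power at 0.07, so the mismatch is conservative. The protocol also says that the size was chosen to balance precision and feasibility, not solved for 80% power.

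Two explanations for the missing 300 are tempting. The enrolment figure of 2000 is a ceiling, compatible with either size, and settles nothing. The Duration section mentions a home visit or phone call for the Aim 3 intervention group, which may be left over from a design with a phone arm, but no Aim 3 text confirms such an arm.

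Finally, the consequence is limited. The SAP covers Aim 4 only, and Aim 3 already has results, so no enrolment or primary analysis changes. That stands, and it makes this a documentation correction. The contradiction in the sample-size sentence is untouched by any of these points.

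**Conclusion.** The contradiction between 1500 and 600 + 600 is certain and rests on no assumption. The stated 0.07 at 80% power is not reproducible from Aim 3's stated inputs: on an assumed two-sided 0.05 with no allowance, it is larger than the detectable difference at either size.

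The match with 600 per arm under Aim 4's allowances, and the lack of one with 750 per arm, suggests that 1500 is the number that does not fit. That is an inference. The Aim 3 text does not say these allowances were used, and Aim 4's 5% attrition is given for its secondary outcomes. The point should be corrected, but it does not threaten the validity of the trial.

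**What to change.** The sponsor should confirm from its records which size was planned, make the total and the arm sizes agree, and state the alpha, sidedness and any noncompliance or attrition allowance actually used, with the matching detectable difference. At two-sided 0.05, that is:

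- for 1200: 0.061 with no allowance, or 0.07 if 11% noncompliance and 5% attrition were used;
- for 1500: 0.055 with no allowance, or 0.063 with the same two allowances.

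Allowances should be reported as they were planned. Since Aim 3 results are known, they should not be chosen now to make 0.07 come out. The cost is a check of the planning records and a short correction to the sample-size text. It needs no added patients and no change of design.

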In all cases, secondary analyses will be performed including potential covariates, which may affect the impact of the intervention. We will look at the association between both the dependent variable of interest and the potential covariate/confounder and between the intervention and the potential covariate or confounder. Those associated with either the dependent variable or the intervention at p<0.15 will be entered into the initial model. Backward elimination will be used, variables significant at p<0.05 and those involved in confounding (i.e., if elimination from the model changes the beta coefficient for the intervention by more than 10%) will be retained in the model. Variables considered as potential covariates are patient age, parent or caregiver age, education, marital status, household income, employment status, and access to primary care.

Additional secondary analyses of the reutilization rate will exclude unforeseen readmissions for newly developed conditions not related to known diseases during the index hospitalization. In addition to the intent to treat analysis, a per-protocol analysis will also be employed. Analysis of secondary outcomes identified through Aim 1 will be tailored to the outcome measure. For example, if parents or caregivers identify days of work missed as an important outcome, our analysis of days of work missed will be restricted to only those parents/caregivers reporting work outside the home. We will take a two-part approach to analysis. First, we will treat it as a binary outcome, comparing the percentage of caregivers that missed at least one day of work during the 30-day follow-up period between the two study arms using logistic regression. Second, we will treat the number of days of work missed as a count outcome and use poisson regression to compare the two study arms. No interim analysis is planned.

Heterogeneity of Treatment Effects:

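### Aim 3 missed-work example: the 14-day questionnaire cannot supply the 30-day window, and Poisson regression is named with no allowance for overdispersion

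*Protocol*

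**What the plan says.** Under DATA ANALYSIS/METHODS, Aim 3, the Protocol says that the analysis of outcomes arising from Aim 1 will be fitted to each measure, and it gives one example. The example applies "if parents or caregivers identify days of work missed as an important outcome" and is limited to caregivers who work outside the home. It then states: "We will take a two-part approach to analysis". The first part is a logistic regression for whether the caregiver "missed at least one day of work during the 30-day follow-up period". The second part is to "treat the number of days of work missed as a count outcome and use poisson regression to compare the two study arms". No window is stated separately for the count. The text mentions no dispersion check, scale parameter, robust variance, alternative count model or offset. It also does not say whether the count part includes caregivers with no missed days.

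Data collection is described under STUDY PROCEDURES, Aims 3 and 4. The Follow-up Questionnaire is "A follow-up questionnaire to assess 14-day post-discharge outcomes", and it "will be conducted in both the control and intervention groups 14-30 days post-discharge". The Medical Record Review paragraph obtains 30-day data from HealthBridge, but only for readmissions and ED revisits. It explains that this lets reutilization be followed to 30 days while the family call takes place at 14 days.

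**The concern.** Missed work can be known only from the caregiver. If the caregiver is asked about 14 days, the 30-day outcome in the analysis text has no data source. If recall instead runs to the day of the call, families contribute different lengths of time and the model has no offset for this.

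The model is the second problem. Poisson regression takes its standard error from the assumption that variance equals mean. Missed days usually break that assumption: many caregivers miss none, and days missed for one illness come in runs. Standard errors would then be too small, and a chance difference between arms could be reported as an effect of the home visit. By contrast, the Protocol does plan a distribution check and possible transformation for parent activation (Aim 3, Working hypothesis 2).

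**Working it through.** The documents give no mean, variance, power or sample size for missed work, so there is no planned figure to reproduce. The Aim 3 sample-size text gives no significance level; two-sided 0.05 is assumed below.

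**1. Window.**
- Analysis period: 30 days (Aim 3 analysis text, binary part).
- Period the questionnaire assesses: 14 days, with the call made on days 14 to 30 (Follow-up Questionnaire).
- Share covered by a 14-day recall: 14/30 = 47%.
- If recall runs to the call, a day-22 call covers 22/30 = 73%, and only a day-30 call covers the whole period.
- The later call described in the Protocol, 31 to 45 days after admission, belongs to Aim 2.

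**2. Overdispersion.** Let φ = variance/mean. The Poisson standard error is 1/√φ of the true one, and the actual two-sided error is 2 × (1 − Φ(1.96/√φ)). The values of φ are assumed; for example, a mean of 2 and an SD of 3 give 9/2 = 4.5.

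| φ | SE ratio 1/√φ | 1.96/√φ | Actual error |
|---|---|---|---|
| 1 | 1.00 | 1.96 | 5% |
| 1.5 | 0.82 | 1.60 | 11% |
| 2 | 0.71 | 1.39 | 17% |
| 3 | 0.58 | 1.13 | 26% |
| 4.5 | 0.47 | 0.92 | 36% |

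This was checked by simulation: 4,000 runs per scenario, no true effect, and 360 working caregivers per arm (an assumed 60% of the 600 per arm in the Aim 3 sample-size text). At φ of 1.5, 2 and 3, the model-based Poisson test rejected in 10.9%, 17.4% and 25.8% of runs. With 40% zeros and the remaining counts drawn as 1 + Poisson(2), φ was 1.86 and the error 15.8%.

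**3. A rough indication from the documents.** The Aim 4 sample-size text assumes an SD of 5 for days back to normal routine, which SAP 1.2 records as 0 to ≥14. Treated as capped at 14, the mean cannot exceed 14, so φ is at least 25/14 = 1.79. The error would be about 14% or more if missed work behaved alike. This is a different outcome and a planning value, so it is only suggestive.

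**4. The direction can reverse.** If the count part takes only caregivers with at least one missed day, counts of the form 1 + Poisson(2) have variance 2 and mean 3, so φ = 0.67. Counts of the form 1 + Poisson(1) have φ = 1/2 = 0.5. The simulated errors were 1.8% and 0.6%, so the standard errors were too large.

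**5. Recall up to the call, without an offset.** With call days spread evenly over 14 to 30 in both arms, exposure has mean 22 and variance (17² − 1)/12 = 24. At an assumed 0.1 or 0.2 missed days per day, φ = 1 + rate × 24/22 = 1.11 or 1.22. The simulated error was 5.8% or 8.0%, and no bias between arms arises because the call timing is the same in both.

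**6. Effect of the remedy.** With a robust variance, the simulated error was 4.5% to 5.6% in every scenario above, in either direction.

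**The case against.** The strongest reply is that this is an illustration. Missed work is analysed only if families name it, and neither document lists it as a selected outcome. The SAP covers Aim 4 only, and its secondary outcomes (SAP 1.2) do not include it. The Protocol's PURPOSE OF STUDY section already reports Aim 3 findings, so a change now may alter no pending analysis. All of this stands, and it keeps the point small.

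Three stronger readings are tempting, and the documents do not support them.

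- **That p-values will be too small.** No mean or variance for missed days is given. The two-part wording leaves open a count model restricted to positive counts, where the error can fall below 5%. Naming Poisson regression also does not rule out a scale parameter or robust variance. Inflation is likely, not shown.
- **That follow-up windows are unequal.** Days 14 to 30 are when the call is made. If every caregiver is asked about the first 14 days, the windows are equal, though shorter than 30 days. A reader might go further, because the abstract's METHODS paragraph times the Aim 3 call from the home visit, which may come up to 4 days after discharge. With recall up to the call, that could give a spurious rate ratio of up to 18/14 = 1.29. But the Follow-up Questionnaire paragraph times the call from discharge in both arms.
- **That Poisson is the plan's method for every day count.** Days back to normal routine gets linear regression in the Protocol's Aim 4 section. In SAP 2.3.3 it gets a generalized linear model with a distribution check.

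The 30-day phrase is also attached to the binary part; for the count it is only implied.

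**Conclusion.** The point holds as a minor one. The window mismatch stands on the text alone: a 30-day missed-work outcome has no described source, and a 14-day recall covers 47% of it. The overdispersion point is conditional. If all working caregivers enter the model and the variance/mean ratio lies between 1.5 and 4.5, the actual error of a nominal 5% test would be about 11% to 36%. Those ratios are assumptions, and the direction depends on who enters the count model, which the Protocol does not say. Nothing here affects the primary outcome or the Aim 4 SAP.

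**What to change.** In the Aim 3 analysis text:

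- Define both the any-missed-day outcome and the count over the first 14 days after discharge for every caregiver. If recall is to run to the call, record the days covered and use their logarithm as an offset in the count model.
- State whether the count model includes all working caregivers or only those with at least one missed day.
- Use Poisson regression with robust (sandwich) variance, or negative binomial regression. Include the Aim 3 stratification factors (acute or chronic underlying illness, and general or surgical service). Robust variance deals with dispersion in either direction; negative binomial deals only with variance above the mean, so robust Poisson is the safer choice if the count part is restricted to positive counts.

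The cost is a shorter window, a few sentences of text and one software option. No extra data are needed unless recall runs to the call. Since this Protocol version already reports Aim 3 findings, any change should be dated and described as made after they were known.
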